### CLINICAL STUDY PROTOCOL SYNOPSIS

TITLE	A randomized controlled clinical trial assessing the efficacy of DEXTENZA, sustained release dexamethasone 0.4 mg insert, when placed within the lower eye eyelid canaliculus in comparison to topical prednisolone acetate following bilateral small incision lenticule extraction (SMILE).
SITE LOCATION(S)	Toledo LASIK & Cataract
PRINCIPAL INVESTIGATOR	[name]
OBJECTIVE(S)	Assessing DEXTENZA efficacy when placed within the lower eyelid canaliculus post SMILE in comparison to topical prednisolone acetate.
STUDY DESIGN	A randomized controlled clinical trial assessing the efficacy of DEXTENZA, sustained release dexamethasone 0.4 mg insert, when placed within the lower eye eyelid canaliculus in comparison to topical prednisolone acetate following bilateral small incision lenticule extraction (SMILE).
STUDY DURATION	3 months
ESTIMATED STUDY COMPLETION DATE	3 months
POPULATION	
Sample Size:	20
Target Population:	Patients undergoing bilateral SMILE
TREATMENT(S)	
Study Drug	Sustained Release Dexamethasone, 0.4 mg
Dose/Route/Schedule:	All patients will receive: First eye randomized for either topical prednisolone acetate (Control eye) or lower eyelid canaliculus DEXTENZA insertion (Study Eye) insertion and the contralateral eye receiving the opposite treatment in the OR following SMILE
ENDPOINT(S)	

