**Primary:**

- Patient preference as measured by Patient Symptoms Questionnaire
- Mean change in pain score
  - Post op pain scores as measured on a scale from 0-10 (Days 1,7,30)
- Mean change in AC cell and flare score
  - Post op inflammation scores as measured on a scale of 0-4 (Days 1,7,30)
    - Absence of cell to be defined as a grade of: 0-0.5
    - Absence of flare to be defined as a grade of: 0-1

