### **3. STUDY DESIGN**

#### **3.1 Study Description and Duration**

This three-month prospective, open-label, single-center, randomized investigator initiated clinical study seeks to investigate the efficacy of DEXTENZA when placed in the lower canaliculus (study eye) compared to topical corticosteroids (control eye) following bilateral SMILE surgery. In addition, the study will evaluate physician assessment of ease of DEXTENZA insertion

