### **4. SELECTION, WITHDRAWAL, AND REPLACEMENT OF PATIENTS**

#### **4.1 Study Population**

The study aims to enroll 20 patients undergoing bilateral SMILE.

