Prospective, Randomized, Fellow Eye-Controlled Study of Postoperative Pain and Inflammation Control with an Intracanalicular Dexamethasone 0.4 mg Ophthalmic Insert Following Small Incision Lenticule Extraction

22NOVEMBER2022

NCT04380857

Statistical Analysis Plan:

No formal power analysis was conducted, and the sample size was set at 40 eyes based on the sample size used in several similar prior studies.^{18–20} Chi-square tests were used to compare proportions and t-tests to compare means. The level of significance was set at 0.05.

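### The documents do not show that the tests, the pairing or the 0.05 level were fixed before outcome data were reviewed

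*SAP*

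**What the plan says.** Below its title and the date "22NOVEMBER2022", the SAP is three sentences, all in the past tense: "No formal power analysis was conducted, and the sample size was set at 40 eyes" (the sentence goes on to cite prior studies), then "Chi-square tests were used to compare proportions and t-tests to compare means", then "The level of significance was set at 0.05". The sample-size sentence carries citation marks 18–20. The SAP has no reference list and the protocol's has three entries, so the paragraph appears to share text with a longer document. The SAP does not state pairing, sidedness, a multiplicity rule, or when the choices were made relative to the data.

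The protocol does not fill the gap. Its contents list runs from section 1 to section 8 without a statistics heading, and section 7 (Study Variables) covers only demographic and baseline characteristics. The pages removed from the public copy precede the synopsis, so their removal does not explain the absence.

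The protocol does fix the following:
- the design: "This three-month prospective, open-label, single-center, randomized investigator initiated clinical study", with one eye on each treatment ("the contralateral eye receiving the opposite treatment in the OR following SMILE");
- three unranked primary endpoint groups: "Patient preference as measured by Patient Symptoms Questionnaire", pain on 0–10, and anterior chamber cell and flare on 0–4, the last two at Days 1, 7 and 30;
- absence of cell as grade 0–0.5 and absence of flare as grade 0–1;
- secondary endpoints: BCVA, UCVA and call-backs per eye.

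**The concern.** A significance level protects against false positives only if the test it belongs to was chosen without regard to the results. A reader who meets the 0.05 level in a document titled as an analysis plan will take it as a commitment made in advance. Here both the tests and the level appear only in a text that reports them as done, and pairing appears nowhere. The trial is open-label, so results by eye could be seen as they accrued.

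Three choices were left open. Cell and flare are listed as a mean change but also have an absence definition, so the same data can go to a t-test or to a chi-square test. The t-test may or may not be paired. With no ranking among the primary endpoints and several visits, any one of many comparisons could be put forward as the result.

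**Working it through.** **1. The plan's own figure.** Protocol section 4.1: "The study aims to enroll 20 patients undergoing bilateral SMILE". 20 patients × 2 eyes = 40 eyes, which agrees with the SAP. The independent units are the 20 patients. No power figure can be reproduced, because the SAP says none was calculated and gives no effect size or SD.

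**2. What is fixed, and where.**

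| Element | Protocol | SAP |
|---|---|---|
| Endpoints | named | not named |
| Days 1, 7, 30 for pain, cell, flare | named | not named |
| Absence cut-offs | cell 0–0.5, flare 0–1 | not mentioned |
| Tests | none | chi-square, t-test, past tense |
| Pairing | design only, no analysis | not stated |
| Alpha | none | 0.05, past tense |
| Ranking or multiplicity rule | none | none |
| Timing relative to the data | not applicable | not stated |

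The undocumented part is the analysis, not the endpoints or visit days.

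**3. Exposure across primary comparisons.** With k tests each at 0.05 and no true difference, the chance of at least one false positive is 1 − 0.95^k if the tests are independent.
- k = 3 (preference, pain, cell/flare): 1 − 0.95³ = 0.143
- k = 4 (cell and flare separate): 1 − 0.95⁴ = 0.185
- k = 10 (preference once; pain, cell and flare at three days each, 1 + 3 × 3): 1 − 0.95¹⁰ = 0.401
- k = 13 (preference at each of the four visits in Table 1, 4 + 9): 1 − 0.95¹³ = 0.487

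Positive correlation between endpoints and visits lowers these figures, so they are upper illustrations.

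**4. Exposure within one inflammation endpoint at one visit.** This was simulated with 20 pairs, no true difference, a latent bivariate normal cut into grades 0, 0.5, 1, 2, 3 and 4, between-eye correlation 0.3 or 0.6, and chi-square without continuity correction. The documents give no grade distribution, so three were assumed. The analyst takes the smallest p-value among a paired t-test, an unpaired t-test and one chi-square test at the protocol's cut-off for that outcome.

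| Assumed grade probabilities (0/0.5/1/2/3/4) | False positives |
|---|---|
| .30/.20/.20/.15/.10/.05 | about 5–7% |
| .70/.15/.10/.03/.015/.005 | about 4–6% |
| .90/.06/.03/.005/.003/.002 | from about 1.5%, staying below 5% |

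Under the first distribution the paired t-test alone gives about 5%. The inflation from choosing the test is therefore small, and with most eyes at grade 0 the error stays below 5%.

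**5. Why pairing has to be settled.** The two eyes of a patient are likely to be positively correlated. Take a true difference δ = 0.5 SD, n = 20 pairs, correlation ρ, two-sided 0.05 and a normal approximation. All of these are assumptions.
- Paired test: power = Φ(δ√(n/(2(1−ρ))) − 1.96)
- Unpaired test on the same data: power = Φ((δ√(n/2) − 1.96)/√(1−ρ)), where δ√(n/2) = 0.5 × √10 = 1.581

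At ρ = 0.3: paired Φ(1.890 − 1.96) = 0.47; unpaired Φ(−0.379/0.837) = 0.33.
At ρ = 0.6: paired Φ(2.500 − 1.96) = 0.71; unpaired Φ(−0.379/0.632) = 0.27.

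The two readings of the SAP's t-test therefore behave quite differently on the same data. The ordinary chi-square test has the same difficulty, because it treats the two eyes of a patient as independent.

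**The case against.** The strongest reply is that past tense and a 2022 date are not evidence of sequence. The documents give no enrolment, database-lock or data-access date, and an earlier plan may exist outside the public files. The citation marks suggest text shared with a manuscript but do not date the choice of test. Open-label conduct means results could be seen, not that the tests were chosen because of them. This stands. A reader might infer that the tests had already been run and that the results can never be called pre-specified; the documents do not establish that.

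A second reply is that the protocol closes much of the freedom. This also stands. A reader might let the analyst choose among both t-tests and chi-square tests at cut-offs above 0, above 0.5 and above 1. With a spread-out grade distribution, that gives about 9% false positives at correlation 0.3 and 7% at 0.6. But the protocol allows one cut-off per outcome and none above 0, and it names mean change as the measure. Those figures also depend on the assumed grade distribution and on omitting the continuity correction. They should not stand as the size of the problem.

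A third reply is that abandoning alpha altogether is a reporting preference. That is fair, and it is not needed here. Calling p-values exploratory rests on firmer ground: several unranked primary endpoints, no multiplicity rule, and no record of timing.

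**Conclusion.** The point holds as a gap in documentation with a practical consequence. The tests and the 0.05 level appear only in a past-tense SAP, the pairing appears in neither document, and the protocol has no statistical section. These documents therefore do not support presenting results at 0.05 as pre-specified, and they do not show that the choices followed the data.

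The exposure lies mainly in the number of unranked primary comparisons: 14% for three to 40% for ten under independence, less with correlation. Choice of test within one inflammation endpoint contributes little, about 1.5–7% false positives across the assumed grade distributions. The estimates remain usable; what changes is how the p-values may be read. The conclusion rests on the public documents alone and would change if a dated plan predating data review were produced.

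**What to change.** 1. Cite a dated record that predates review of outcome data and fixes the tests, pairing and alpha. If there is none, state in the SAP and the report that these are not shown to be pre-specified.
2. In either case, report every protocol-listed endpoint at every listed visit: pain, cell and flare at Days 1, 7 and 30, preference and visual acuity at the visits scheduled in Table 1, and call-backs per eye.
3. Give each a within-patient estimate with a 95% interval. For means, use the average between-eye difference and a paired t-test. For proportions by eye, use the paired difference in proportions, with McNemar's test in place of the ordinary chi-square. Preference is one answer per patient, so give the proportion of patients preferring each treatment with an exact binomial interval.
4. Present p-values as exploratory, because the primary endpoints are unranked and there is no multiplicity rule.
5. If the report discusses the effect of test choice, restrict it to the protocol's cut-offs and state the grade distribution as an assumption.

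The cost is a change of wording and a re-analysis of existing data with standard paired methods. No new data are needed. The downside is a weaker claim than significance at 0.05.

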**2. STUDY OBJECTIVES**

**2.1 Primary Objective**

To determine the effect of dexamethasone insert through Week 12 as measured by:

- Patient preference
- Mean change in pain score
  - Post op pain scores as measured on a scale from 0-10 (Days 1,7,30)
- Mean change in AC cell and flare score
  - Post op inflammation scores as measured on a scale of 0-4 (Days 1,7,30)
    - Absence of cell to be defined as a grade of: 0-0.5
    - Absence of flare to be defined as a grade of: 0-1

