**[name] STUDY**

**Table 1 Schedule of Events**

Study Procedure	Screening/ Baseline	Surgical Visit Day 0	Day 1	Day 7	Day 30	3 MTH post-op	Early Termin- ation
Visit	VISIT 1	VISIT 2	VISIT 3	VISIT 4	VISIT 5	VISIT 6	
Windows for Visits	(Day -30 to -1)			+/- 3 day	+/- 5 days	+/- 7 days	
Inclusion/Exclusion	x						
Informed Consent	x						
Demographics	x						
Medical History and Concurrent Illnesses	x						
Concomitant Medications	x	x	x	x	x	x	
Distance UCVA testing	x		x	x	x	x	
BCVA (ETDRS at 4m)	x			x	x	x	
Ophthalmic Examination (w or w/o dilated fundus exam)	x	x	x	x	x	x	
Pentacam	x						
Intraocular Pressure	x			x	x	x	
Indicate the incision type, location, and size (mm)			x	x	x	x	
Record any surgical complications	x	x	x	x	x	x	
Subject reported AEs prior to or after surgery	x	x	x	x	x	x	
Intracanalicular dexamethasone insert*		x					
Patient Treatment Preference			x	x	x	x	
Ocular Pain Assessment	x		x	x	x	x	
Anterior chamber cell count	x		x	x	x	x	
Anterior chamber cell flare	x		x	x	x	x	
Insert Visualization		x	x	x	x	x	

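### Three or four primary endpoints share one 0.05 level with no primary visit, order, adjustment or success rule, so the false-positive rate of the primary conclusion is not controlled

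*SAP*

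**What the plan says.** The protocol synopsis (Primary) and section 2.1 give the same primary list, unranked:

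- Preference: "Patient preference as measured by Patient Symptoms Questionnaire".
- Change in pain: "Post op pain scores as measured on a scale from 0-10 (Days 1,7,30").
- AC inflammation: "Mean change in AC cell and flare score", with "Post op inflammation scores as measured on a scale of 0-4 (Days 1,7,30"). Cell and flare have different thresholds for absence, so they may be meant as two outcomes.

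The SAP's statistical content is three sentences. On power it says "No formal power analysis was conducted", and it sets the size at 40 eyes, which matches the protocol's 20 patients with both eyes treated. On tests it says "Chi-square tests were used to compare proportions and t-tests to compare means". On error it says "The level of significance was set at 0.05".

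Neither document states a primary visit, a testing order, a multiplicity adjustment, or whether one or all primaries must succeed. Nor does either say whether tests are two-sided or whether the t-tests are paired.

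The preference visits also differ within the protocol. Table 1 marks "Patient Treatment Preference" at all four post-operative visits. Section 5.2.1 lists the symptoms questionnaire only at Visits 4 to 6, and a differently named patient assessment at Day 1.

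**The concern.** With several primaries and no decision rule, a result below 0.05 on any of them could be presented as the answer to the primary objective. The endpoint or visit could also be chosen after the data are seen. The stated 0.05 is then the error rate of each single test, not of the primary conclusion. This matters more here because the study is open-label (protocol section 3.1), and preference and pain are reported by patients who know which eye had which treatment.

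**Working it through.** **Reproducing the plan's figures.** 20 patients × 2 eyes = 40 eyes, as stated. No effect size, SD or power is given, so nothing else can be reproduced.

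**Inputs from the documents.** Level 0.05; 20 pairs of eyes; primary outcomes preference, pain, cell and flare; pain and inflammation scored on Days 1, 7 and 30.

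**Assumptions.** Two-sided tests, each of true size 0.05; no true difference on any endpoint; any one significant result counts. The documents give no correlations, so ranges are shown.

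**Counting tests.** One per endpoint gives 3, or 4 with cell and flare separate. The text does not say that each visit is a separate test, but nothing prevents it. With one preference test, by-visit testing gives 1 + 3 + 3 = 7, or 1 + 3 + 3 + 3 = 10 with cell and flare separate.

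**False-positive rate for m tests.** Independent: 1 − 0.95^m. For m = 3, 1 − 0.857 = 0.143; for m = 4, 1 − 0.815 = 0.185. Correlated: numerical integration over equicorrelated normal statistics.

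| Tests | Independent | Correlation 0.7 |
|---|---|---|
| 3 | 14.3% | 10.9% |
| 4 | 18.5% | 13.0% |
| 7 | 30.2% | 17.8% |
| 10 | 40.1% | 21.3% |

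**If preference truly differs.** A significant preference result is then not false, and 2 to 3 null tests remain. Independent: 1 − 0.95² = 9.8% and 1 − 0.95³ = 14.3%. At correlation 0.7: 8.3% and 10.9%.

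**If only results favouring the insert count.** The level is 0.025 per test. For 3 and 4 tests, 1 − 0.975^m = 7.3% and 9.6% if independent; 5.5% and 6.5% at correlation 0.7.

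**If the t-tests are run unpaired on fellow eyes.** They are conservative when the two eyes of a patient are positively correlated. I simulated the size s for 20 pairs, then took 1 − 0.95 × (1 − s)^k, with k = 2 or 3 t-tests and a valid 5% preference test.

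| Between-eye correlation | s | 3 tests | 4 tests |
|---|---|---|---|
| 0.2 | 3.0% | 10.6% | 13.3% |
| 0.3 | 2.1% | 8.9% | 10.9% |
| 0.5 | 0.75% | 6.4% | 7.1% |

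**If preference is tested as two samples of 20 eyes.** A split of x to 20 − x among 20 patients becomes x/20 against (20 − x)/20. The uncorrected chi-square is 3.6 at x = 13 and 6.4 at x = 14, so 14 to 6 is enough (critical value 3.84). Under a true 50:50 preference, a split of 14 to 6 or more extreme in either direction has probability 11.5%. With independent 5% tests elsewhere, the total is 1 − 0.885 × 0.95² = 20% for 3 tests and 1 − 0.885 × 0.95³ = 24% for 4.

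**The case against.** The strongest reply is that the rates depend on a rule the documents do not contain. Section 2.1 lists the outcomes as measures of one objective and does not say that one is enough; if all had to succeed, there would be no inflation. That is correct, and it is why the figures are conditional. But no all-must-succeed rule is written either, so the plan does not exclude the any-one reading.

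Second, the headline range takes every null as true, including preference. The protocol's introduction and rationale rest on sparing patients the burden of drops, so a true 50:50 preference may be the least plausible null. This stands, and it lowers the range to 10% to 14% if independent, or 8% to 11% at correlation 0.7. It does not bring it to 5%.

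Third, this is a small single-centre study that openly declares no power analysis, and the SAP reads as if the work were done. Neither document calls the study exploratory, though: efficacy is the stated aim and a significance level is set. If the analysis is complete, what remains is a matter of labelling and full reporting.

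A reader might infer more than the documents support:

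- That every visit is a separate primary test, so the error is 30% to 40% or higher. The text neither says this nor rules it out. Testing preference at every visit as well would give 9 or 10 tests with cell and flare combined, or 12 or 13 with them separate. Even these counts leave out the absence-of-cell and absence-of-flare proportions and the 3-month scores.
- That the independence figures are a ceiling. They are not: a two-sample chi-square on preference exceeds them.
- That unpaired testing brings the rate safely down. The amount depends on a between-eye correlation that the documents do not give.

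**Conclusion.** The concern holds in conditional form. If any one significant primary result can be the answer and there is no true difference on any endpoint, one valid two-sided 0.05 test per endpoint carries a 14% to 19% chance of at least one false positive if independent, and 11% to 13% at an assumed correlation of 0.7.

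Other readings move the rate both ways: down to about 5% to 10% if only favourable results count, up to 20% to 24% with the two-sample preference test, and higher if visits are tested separately. The reductions come from how the tests happen to be run or read, not from a rule in the plan. The documents do not show that a false claim was made or that an endpoint was selected; they show that nothing prevents it. This should be fixed, and the gap itself is plain from the text.

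**What to change.** In the SAP, define one test per primary endpoint at one named visit or summary:

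- **Pain, cell and flare:** a paired t-test on the within-patient between-eye difference in change from baseline.
- **Preference:** one choice per patient at Day 30, a visit covered by both Table 1 and section 5.2.1 (Visits 4 to 6), with an exact binomial test against 50%.
- **Decision rule:** Holm across the four tests at overall two-sided 0.05, with the objective claimed only for endpoints that pass.
- **Other visits:** estimates with 95% confidence intervals, labelled descriptive.

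Averaging Days 1, 7 and 30 is one possible summary, not a requirement; it would dilute an effect confined to Day 1. Handling of missing visits, scores after rescue and no-preference answers should also be stated. The documents do not dictate these choices.

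**Cost if the data are not yet analysed.** SAP wording, and some power. At Holm's first step (0.05/4 = 0.0125), the effect detectable with 80% power in 20 pairs rises from 0.66 to 0.81 SD of the paired difference, and power at 0.66 SD falls from 80% to 58%. Preference needs 16 of 20 (p = 0.012) instead of 15 of 20 (p = 0.041).

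**If the data are already analysed.** Report every primary test at every visit, label any multiplicity rule post hoc, and describe the results as exploratory. That costs a re-analysis and recovers no confirmatory claim.
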